8.3.1 Estimands and Intercurrent Events for Phase 1/2/3a, Phase 3b and Phase 3c

Possible intercurrent events (IcEvs) are presented in [Table 14](#).

Table 14 Intercurrent Event Types

Label	Intercurrent Event Type
IcEv1 (Death not due to COVID-19)	Death due to any cause other than COVID-19 associated.
IcEv2 (Non-study COVID-19 vaccine)	Use of non-study COVID-19 vaccine.
IcEv3 (Early infection)	Positive RT-PCR test or seropositivity for antinucleocapsid antibody or neutralizing antibody (as assessed by sVNT for Phase 1/2/3a and MNT for Phase 3c) indicating exposure to SARS-CoV-2 prior to vaccination or SARS-CoV-2 infection prior to 7 days (inclusive) after the second study vaccination dose (Day 35). Note: for immunogenicity endpoints, Day 57 is the watershed for early infection.
IcEv4 (Study infection)	Develops virologically confirmed SARS-CoV-2 infection, with or without COVID-19 symptoms more than 7 days after second study vaccine dose (\geq Day 36).
IcEv5 (Confounding On-study Medications)	Receives any of the following concomitant medications/vaccines prior to the time point for which the analysis is being performed: 
• Live vaccines within 28 days before or after any study vaccination• Systemic (oral, intravenous, intramuscular or subcutaneous) corticosteroids given at any study time point prior to the timepoint at which the analysis is being performed• Blood products or immunoglobulins given at any study time point prior to the timepoint at which the analysis is being performed• Immunosuppressive medications, including cytotoxic medication for cancer or autoimmune disease, given at any study time point prior to the timepoint at which the analysis is being performed

Abbreviations: COVID-19=coronavirus disease 2019; IcEv=intercurrent event; SARS-CoV-2=severe acute respiratory syndrome coronavirus 2

Attributes for the principal safety and immunogenicity estimands for Phase 1/2/3a, 3b and 3c with strategies for IcEvs are presented in the tables below.

Table 15 Estimands for Phase 1/2/3a Substudy and Phase 3c Substudy Primary, Secondary and Exploratory Immunogenicity Endpoints

Estimand Label	Estimand 1 (immunogenicity)
Estimand Description	NAb by surrogate virus neutralization test (primary for Phase 1/2/3a), NAb by PRNT50 (secondary for Phase 1 and 2 only), NAb by pseudovirus microneutralization test (MNT; secondary for Phase 3c) and BAb (secondary for Phase 1/2/3a and Phase 3c) responses at defined time points following vaccination (as defined in Sections 3.1.1 , 3.1.2 and 3.3.2) with ARCT-154 or placebo. These endpoints will be assessed based on responses at Day 57. International units (i.e., the WHO/NIBSC international reference standard) will be used if available.

Table 15 Estimands for Phase 1/2/3a Substudy and Phase 3c Substudy Primary, Secondary and Exploratory Immunogenicity Endpoints

Target Population	Vaccinated participants (as defined by eligibility criteria) in Phases 1, 2, 3a and 3c (Phase 3c-1 participants only). The population includes participants without evidence of COVID-19, SARS-CoV-2 infection, or nucleocapsid antibody positivity on or prior to Day 57.
Endpoint	Phase 1/2/3a: NAb and BAb responses as defined in Sections 3.2.1 and 3.2.2 Phase 3c: NAb and BAb responses as defined in Section 3.3.2
Treatment Conditions	Phase 1, 2 and 3a: ARCT-154 dose 5 µg or placebo administered on Day 1 and Day 29. Phase 3c: ARCT-154 dose 5 µg or ChAdOx1 administered on Day 1 and Day 29.
Population-Level Summary	The following will be assessed 
 • Geometric mean concentrations for NAb and BAb • The geometric mean ratio (ARCT-154 /Placebo and ARCT-154 / ChAdOx1) for NAb and BAb concentrations • Proportion of participants in each study vaccine group that demonstrate seroconversion (as defined by 4-fold increase in antibody concentration [based on international units, if available] from baseline). • Geometric mean fold rise (GMFR) for NAb and BAb
Intercurrent Event (IcEv) Strategy	
IcEv1 (Death not due to COVID-19)	Hypothetical strategy
IcEv2 (Non-study COVID-19 vaccine)	Treatment policy strategy
IcEv3 (Early infection)	Principal stratum strategy
IcEv4 (Study infection)	Principal stratum strategy
IcEv5 (Confounding On-study Medications)	Treatment policy strategy
Rationale for Strategies	IcEv 2 and IcEv5 could be potentially confounding to the analysis of the endpoint and result in censoring of the participant for all endpoint assessments after the time of the IcEv treatment policy). IcEv4 and IcEv5 could also be potentially confounding but it is more difficult to determine the precise timing of these events, so a principal stratum strategy is used to exclude these participants from immunogenicity analyses.

Abbreviations: NAb=neutralizing antibody; BAb=binding antibody; PRNT50=plaque reduction neutralization test at 50% reduction; COVID-19=coronavirus disease 2019; IcEv=intercurrent event; SARS-CoV-2=severe acute respiratory syndrome coronavirus 2

Table 16 Estimands for Primary, Secondary and Exploratory Efficacy Analyses

Estimand Label	Estimand 2 (Vaccine Efficacy)
Estimand Description	
 The proportion of participants (and 95% confidence interval) with virologically confirmed COVID-19 (Appendix 2) detected after 7 days post the second study vaccine dose. Proportion of participants (and 95% confidence interval) with virologically confirmed COVID-19 (Appendix 2) detected at any time after first vaccine dose
Target Population	Eligible participants who have received both doses of study vaccine in the initial series. The population includes participants without evidence of COVID-19, SARS-CoV-2 infection, or nucleocapsid antibody positivity on or prior to Day 35.
Endpoint	
Incidence of COVID-19/severe COVID 19/death due to COVID-19 (dependent on the endpoint concerned (Section 3)) detected after 7 days post the second study vaccine dose and based upon virologically confirmed COVID-19 (Appendix 2)
 
Additional endpoints will include proportion of participants with virologically confirmed COVID-19 (Appendix 2) detected at any time after first vaccine dose.

Treatment Conditions	
Phase 1, 2, 3a and 3b: ARCT-154 dose 5 µg or placebo administered on Day 1 and Day 29.
 
Phase 3c: ARCT-154 dose 5 µg or ChAdOx1 administered on Day 1 and Day 29.

Population-Level Summary	
The proportion of participants (and 95% confidence interval) with virologically confirmed COVID-19 cases (Appendix 2) detected after 7 days post the second study vaccine dose.
 
Additional exploratory endpoints will include proportion of participants with virologically confirmed COVID-19 (Appendix 2) detected at any time after first vaccine dose.

Intercurrent Event (IcEv) Strategy	
IcEv1 (Death not due to COVID-19)	Hypothetical strategy
IcEv2 (Non-study COVID-19 vaccine)	Hypothetical strategy
IcEv3 (Early infection)	Principal stratum strategy
IcEv4 (Study infection)	Composite strategy
IcEv5 (Confounding On-study Medications)	Hypothetical strategy
Rationale for Strategies	Early infection (IcEv3) results in complete exclusion from analyses because prior to Day 36, the vaccine may not have achieved full efficacy. Additional exploratory analyses are performed where participants with early infection occurring after Day 1 but before Day 36 are included.

Table 17 Estimands for Primary Safety Analyses for Phase 1/2/3a, Phase 3b, Phase 3c and Pooled Cohorts

Estimand Label	Estimand 3 (Safety – Unsolicited AEs/AEs leading to discontinuation or withdrawal/MAAE/SAE)
Estimand Description	Count and percentage of vaccinated participants who would develop unsolicited AEs, AEs leading to discontinuation/withdrawal, MAAEs, and SAEs. These will be evaluated with each dose of study vaccine, ARCT-154 or placebo.
Target Population	The population who are enrolled in the study and receive any dose of study vaccine (Phase 1, 2, 3a, 3b, 3c-1, and 3c-2 participants)
Endpoint	Occurrence of unsolicited AEs will be analyzed up to 28 days after each study vaccine administration. Occurrence of AEs leading to discontinuation/withdrawal, MAAEs, or SAEs will be analyzed up to Day of Switchover/Further Study Vaccine, receipt of non-study vaccine, early withdrawal, or last on-study assessment visit, whichever comes first. Occurrence of AEs leading to discontinuation/withdrawal, MAAEs and SAEs after the Switchover/Further Study Vaccine will be recorded and summarized for the interval from the switchover/Further Study Vaccine up to Day 394 (Phase 1/2/3a and Phase 3b only). For Phase 1/2/3a and 3b, AEs in participants who do not undergo Switchover/Further Study Vaccine will be recorded for the interval from Day 92 up to Day 394
Treatment Conditions	Phase 1/2/3a and 3b: ARCT-154 dose 5 µg or placebo administered on Day 1, Day 29, or at Switchover/Further Study Vaccine (Day 92 and Day 120) Phase 3c: ARCT-154 dose 5 µg or ChAdOx1 administered on Day 1 and Day 29.
Population-Level Summary	Percentage of vaccinated participants who develop each type of AE
Intercurrent Event (IcEv) Strategy	
IcEv1 (Death not due to COVID-19)	Composite strategy
IcEv2 (Non-study vaccine)	Treatment policy strategy
IcEv3 (Early infection)	Composite strategy
IcEv4 (Study infection)	Composite strategy
...IcEv5 (Confounding On-study Medications)	Composite strategy
Rationale for Strategies	Events occurring after IcEv2 could contribute spurious safety data so a treatment policy is used for these events and events occurring after this IcEv's will be summarized separately. Sensitivity analyses will be conducted in the ITT population where these events will be included (composite strategy).

Table 17 Estimands for Primary Safety Analyses for Phase 1/2/3a, Phase 3b, Phase 3c and Pooled Cohorts

Estimand Label	Estimand 4 (Reactogenicity – Solicited AEs)
Estimand Description	Count and percentage of vaccinated participants who would develop solicited AEs. These will be evaluated after vaccination on Day 1 and Day 29, ARCT-154 or placebo.
Target Population	Vaccinated adults providing at least 1 Diary assessment, including reported absence of solicited events.
Endpoint	Occurrence of solicited AEs: Solicited AEs within 7 days after study vaccination on Day 1 and Day 29, by Toxicity Grade (Appendix 4)
Treatment Conditions	Placebo or ARCT-154 at dose 5 µg administered on Day 1 and Day 29.
Population-Level Summary	Percentage of vaccinated participants who provide at least 1 safety assessment.
Intercurrent Event (IcEv) Strategy	
IcEv1 (Death not due to COVID-19)	Composite strategy
IcEv2 (Non-study vaccine)	Treatment policy strategy
IcEv3 (Early infection)	Treatment policy strategy
IcEv4 (Study infection)	Composite strategy
...IcEv5 (Confounding Concomitant Medications)	Treatment policy strategy
Rationale for Strategies	Events occurring after IcEv2, IcEv3 and IcEv5 could contribute spurious reactogenicity data so a treatment policy is used for these events and events occurring after these IcEv's will be summarized separately.

Abbreviations: AE=adverse event; COVID-19=coronavirus disease 2019; IcEv=intercurrent event; MAAE=medically attended adverse event; SAE=serious adverse event; SARS-CoV-2=severe acute respiratory syndrome coronavirus 2.

8.4 Statistical Hypothesis

8.4.1 Phase 1/2/3a Substudy Statistical Hypothesis

For the seroconversion rate primary immunogenicity objective, the null hypothesis ($H_0^{\text{Immunogenicity}}$) is that the lower bound of the 95% CI for ARCT-154 seroconversion rate (SC^{154}) is \leq seroconversion rate for placebo (SC^{Placebo}); i.e., $H_0^{\text{Immunogenicity}}$: lower bound 95% CI for $SC^{154} \leq SC^{\text{Placebo}}$. Hence the Phase 1/2/3a part of the study will be considered to meet the primary immunogenicity objective if the lower bound of the 95%CI for $SC^{154} > SC^{\text{Placebo}}$.

There is no hypothesis testing for safety data analysis. Where statistical methods are applied, the emphasis will be on estimation with 95% CIs.

8.4.2 Phase 3b Statistical Hypothesis

The overall primary endpoints for the study are evaluated in the Phase 3b population as follows:

- The overall primary efficacy endpoint for the study is vaccine efficacy as evaluated in the Phase 3b Modified Intent to Treat (mITT) population
- The overall primary safety endpoints are those evaluated in the Phase 3b Safety Analysis Set (SAS) and Phase 3b Reactogenicity Analysis Set (RAS)

There is no hypothesis testing for safety data analysis. Where statistical methods are applied, the emphasis will be on estimation with 95% CIs.

The primary statistical analyses for VE will be performed using virologically confirmed COVID-19 cases as adjudicated in a blinded fashion by the Independent Adjudication Committee according to definitions provided in [Appendix 2](#). This analysis of the VE will be based on the Phase 3b mITT analysis set (Section [8.2](#)). Sensitivity analyses will be performed in the Phase 3b PP set.

The null hypothesis (H_0^{Efficacy}) as follows: H_0^{Efficacy} : $VE \leq 30\%$

VE is estimated as 1-HR, where HR is the hazard ratio, and will be presented together with 95% CIs. The primary efficacy objective will be met if the lower limit of the 95% CI for VE exceeds 30%.

Under the assumptions of proportional hazards over time and a 50% reduction in hazard rate (50% VE) and with 1:1 randomization of ARCT-154 and placebo, a total of 372 confirmed COVID-19 cases will provide approximately 90% power to reject the null hypothesis (H_0 : $VE \leq 30\%$), using a log-rank test statistic with a 1-sided false positive error rate of 0.025.

8.4.3 Phase 3c Substudy Statistical Hypotheses

There is no hypothesis testing for primary Phase 3c safety objective. Where statistical methods are applied, the emphasis will be on estimation with 95% CIs.

For the primary Phase 3c immunogenicity noninferiority objective the null hypothesis is as follows:

$$H_0^{GMR}: R \leq NIM$$

Where R is the ratio of GMC (i.e., GMC for ARCT-154 arm / GMC for the ChAdOx1 arm) and NIM is the acceptable noninferiority margin (0.67). The null hypothesis will be rejected if the lower bound of the 95% confidence interval for GMR is > 0.67.

A sequential/hierarchical testing procedure will be used to control type 1 error rate over the Phase 3c primary immunogenicity noninferiority endpoint and the secondary endpoints such that the Phase 3c secondary immunogenicity endpoints will only be tested if the null hypothesis is rejected for the primary endpoint and Phase 3c secondary endpoints numbers 1 through 5 will be tested sequentially using the same hierarchical test procedure with each endpoint only being tested if the null hypothesis is rejected for the preceding endpoint.

For secondary endpoints based on the ratio of GMC (i.e., GMR; secondary endpoints 1, 4, 5):

- The null hypothesis for noninferiority and the grounds for rejecting the null hypothesis is as stated for the primary Phase 3c endpoint.
- The null hypothesis for superiority of ARCT-154 to ChAdOx1 arm (ie, GMC of ARCT-154 statistically significantly higher than ChAdOx1) is as follows:

$$H_0^{GMR}: R \leq 1$$

The null hypothesis will be rejected if the lower bound of the 95% confidence interval for GMR is > 1.0

For secondary endpoints based on seroconversion rate (Secondary endpoints 2 and 3):

- The null hypothesis for noninferiority of the ARCT-154 arm to the ChAdOx1 arm ($H_0^{Seroconversion}$) is as follows:

$$H_0^{Seroconversion}: SC^{154} - SC^{ChAdOx1} \leq D0$$

Where SC^{154} is the proportion seroconverting in the ARCT-154 group, $SC^{ChAdOx1}$ is the proportion seroconverting in the ChAdOx1 group and D0 is the acceptable noninferiority margin (-10.0%). Seroconversion is defined as: 4-fold increase in concentration from baseline. The 95% confidence interval of the difference between two proportions will be calculated using the method of Miettinen-Nurminen ([Miettinen 1985](#)). International units (i.e., the WHO/NIBSC international reference standard) will be used if available.

The null hypothesis will be rejected if the lower bound of the 95% confidence interval (CI) of the difference between neutralizing antibody seroconversion rates (ARCT-154 group minus ChAdOx1 group) excludes the non-inferiority margin of -10%.

8.4.4 Pooled Analyses Statistical Hypotheses

Pooled analyses are performed as sensitivity analyses to the Phase 3b safety and efficacy primary endpoints. As such, Pooled analyses of efficacy and safety are nominally declared as primary, secondary, and exploratory to align with the equivalent endpoints in the Phase 3b population, but any statistical analysis performed will be nominal. The pooled endpoints will be evaluated in the same fashion as the equivalent analyses in the Phase 3b populations.

8.5 Sample Size Determination

The sample size for the study overall is driven by the sum of the sample size assumptions for the individual phases of the study, as outlined in the subsections below.

8.5.1 Sample Size for Phase 1/2/3a Substudy

Data from Phases 1, 2 and 3a will be pooled up to Day 92 for safety analyses, which will be performed in the Phase 1/2/3a SAS and Phase 1/2/3a RAS (Section 8.2). The total sample size for Phase 1/2/3a is primarily driven by the size of safety database required at the time of potential EUA application. With approximately 750 participants randomized in Phases 1, 2 and 3a to receive ARCT-154 for the Phase 1/2/3a primary safety analysis, if the incidence rate of an adverse event is 1.0%, the probability to detect one event in 750 vaccinated participants is >99%, based upon the following formula:

$$p = 1 - (1 - R)^N$$

where R = incidence rate and N = sample size

Data from Phases 1, 2 and 3a will be pooled up to Day 92 for immunogenicity analyses, which will be performed in the Phase 1/2/3a IAS (Section 8.2). The primary immunogenicity endpoint is defined as the proportion of participants in each study vaccine group that demonstrate seroconversion (defined as: 4-fold increase in titer from baseline) by surrogate virus NAb assay at Day 57. Sensitivity analyses will be performed in the Phase 1/2/3a per protocol (PP) set.

The null hypothesis is $H_0^{\text{Immunogenicity}}$: lower bound 95% CI for $SC^{154} \leq SC^{\text{Placebo}}$. A sample size of 750 and 250 participants in the ARCT-154 and placebo groups respectively will provide greater than 90% power to exclude the null hypothesis with a 1-sided type 1 error rate of 0.025 assuming that 10% of participants are excluded from the analysis (for example due to baseline seropositivity), and that $SC^{154} > 50\%$ and $SC^{\text{Placebo}} \leq 10\%$.

8.5.2 Sample Size for Phase 3b

The primary safety endpoints will be evaluated in the Phase 3b SAS and the Phase 3b RAS (Section 8.2). With a sample size of ~16,000 participants randomized and with approximately 8,000 participants randomized in the study to receive ARCT-154 for the primary safety analysis, if the incidence rate of an adverse event is 0.1%, the probability to detect one event in 8,000 vaccinated participants is >99.9%, based upon the following formula:

$$p = 1 - (1 - R)^N$$

where R = incidence rate and N = sample size

For the overall primary efficacy objective of the study, the null hypothesis is that the VE of ARCT-154 to prevent first occurrence of polymerase chain reaction (PCR)-confirmed COVID-19 is $\leq 30\%$ (ie, H_0^{efficacy} : $VE \leq 0.3$).

The primary efficacy objective will be met if the lower limit of the 95% CI for VE exceeds 30%. VE is defined as the percent reduction in the hazard of the primary endpoint (ARCT-154 versus placebo). Equivalently, the null hypothesis is as follows:

- H_0^{efficacy} : $HR > 0.7$ (equivalently, proportional hazards $VE \leq 0.3$)

A Cox proportional hazard model will be used to assess the magnitude of the study group difference (ie, HR) between ARCT-154 and placebo at a 1-sided 0.025 significance level. Data will be presented overall and by the stratification factors described in Section 8.6.

Under the assumption of proportional hazards over time and with 1:1 randomization of ARCT-154 and placebo, a total of 372 COVID-19 cases will provide approximately 90% power to detect a 50% reduction in hazard rate (50% VE), rejecting the null hypothesis with a 1-sided false positive error rate of 0.025.

The study will be considered positive at the primary analysis if the one-sided p-value for rejecting $HR \geq 0.7$ is less than or equal to 0.025.

8.5.3 Sample Size for Phase 3c Substudy

Immunogenicity endpoints will be evaluated in participants in the Phase 3c-1 IAS (Section 8.2). Sensitivity analyses will be performed in the Phase 3c PP set. For the primary immunogenicity noninferiority endpoint of neutralizing antibody (using the pseudovirus microneutralization assay [MNT]) geometric mean ratio (GMR), assuming a GMR of ≥ 0.9 and a coefficient of variation of variation of 4.6, a sample size of 800 participants in Phase 3c-1 will provide greater than 90% power to exclude a non-inferiority boundary of 0.67 based on the use of a one-sided test at the alpha=0.025 level of significance, accounting for a dropout rate of approximately 20-25% due to the national COVID-19 vaccination campaign in Vietnam.

The primary safety endpoints of Phase 3c will be conducted in the Phase 3c Safety Analysis Set and Phase 3c Reactogenicity Analysis Set (Section 8.2). With a sample size of approximately 2,400 participants randomized and with approximately 1,200 participants randomized in the study to receive ARCT-154 or ChAdOx1 for the safety analysis, based upon the following formula, if the incidence rate of an adverse event is 0.1%, the probability to detect one event in 1,200 vaccinated participants is 69.9% and if the incidence rate is 1.0% the probability is more than 99%:

$$p = 1 - (1 - R)^N$$

where R = incidence rate and N = sample size

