--	--

	
formula, if the incidence rate of an adverse event is 0.1%, the probability to detect one event in 1,200 vaccinated participants is 69.9% and, if the incidence rate is 1.0%, the probability is more than 99%:
 $p = 1 - (1 - R)^N$ 
where R = incidence rate and N = sample size
 
The primary immunogenicity noninferiority endpoint for Phase 3c is the ratio of geometric mean concentrations (geometric mean ratio or GMR) for neutralizing antibody (using the pseudovirus microneutralization assay [MNT]) concentration and will be evaluated in participants in the Phase 3c-1 Immunogenicity Analysis Set (Section 8.2). Sensitivity analyses will be performed in the Phase 3c PP set. International units (i.e., the WHO/NIBSC international reference standard) will be used if available.
 
The null hypothesis (H_0^{GMR}) for the primary endpoint is as follows:
 $H_0^{\text{GMR}}: R \leq \text{NIM}$ 
Where R is the ratio of GMC (i.e., GMC for ARCT-154 arm / GMC for the ChAdOx1 arm) and NIM is the acceptable noninferiority margin (0.67). The null hypothesis will be rejected if the lower bound of the 95% confidence interval for GMR is > 0.67.
 
Assuming a GMR of ≥ 0.9 and a coefficient of variation of 4.6, a sample size of 800 participants in Phase 3c-1 will provide greater than 90% power to exclude a non-inferiority boundary of 0.67 based on the use of a one-sided test at the alpha=0.025 level of significance, accounting for a dropout rate of approximately 20-25% due to the national COVID-19 vaccination campaign in Vietnam.
 
A sequential/hierarchical testing procedure will be used to control type 1 error rate over the Phase 3c primary endpoint and the secondary endpoints such that the secondary immunogenicity endpoints will only be tested if the null hypothesis is rejected for the primary endpoint and Phase 3c secondary endpoints numbers 1 through 5 will be tested sequentially using the same hierarchical test procedure with each endpoint only being tested if the null hypothesis is rejected for the preceding endpoint.
 
Missing Data
 
How missing data points will be handled will be described in the SAP.

--	--

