3.3 Phase 3c Substudy

3.3.1 Phase 3c Substudy Primary Objectives and Endpoints

The primary objectives and endpoints for Phase 3c are presented in [Table 8](#). The first approximately 1,500 participants in Phase 3c will be enrolled into Phase 3c-1, the group that will have blood drawn for immunogenicity assessments. Data from 800 participants in this subgroup will be used to establish the noninferiority of immunogenicity of ARCT-154 vaccine as compared to ChAdOx1. Samples from the remaining 700 participants in Phase 3c-1 will be retained for potential future immunological testing, for example against newly emerging variants of concern. Safety evaluations will be based on all participants in Phase 3c.

Table 8 Phase 3c Substudy Primary Objectives and Endpoints

Phase 3c Primary Objectives	Endpoint Description
1. To assess the safety and reactogenicity of ARCT-154 and ChAdOx1	
Safety will be evaluated in all participants in the Phase 3c SAS and will be summarized for each vaccination as number and percentage of participants with:
 
 • Any unsolicited AE starting within 28 days after each study vaccine administration, summarized by severity and relationship to study vaccine. • Any medically attended adverse event (MAAE), serious adverse event (SAE), or AE leading to discontinuation/withdrawal through Final Visit/Early Termination (ET) summarized by relationship to study vaccine. 
Reactogenicity will be evaluated in participants in the Phase 3c RAS and will be summarized following vaccinations on Day 1 and Day 29 only as the number and percentage of participants with:
 
 • Any solicited local or systemic AE starting within 7 days after each study vaccine administration by toxicity grade.

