4.1 Number of Participants

Enrollment of approximately 19,400 participants across all phases of the study is planned, as follows:

- Phase 1: 100 (75 ARCT-154:25 placebo per study group)
- Phase 2: approximately 300 (225 ARCT-154:75 placebo per study group)
- Phase 3a: approximately 600 (450 ARCT-154:150 placebo per study group)
- Phase 3b: approximately 16,000 (8,000 per study group)
- Phase 3c: approximately 2,400 (~1,200 per study group)
 - o The first approximately 1,500 participants will be enrolled into Phase 3c-1, the group that will have blood drawn for immunogenicity assessments. Data from 800 participants in this subgroup will be used to establish the noninferiority of immunogenicity of ARCT-154 vaccine as compared to ChAdOx1
 - o The remaining ~900 participants will form Phase 3c-2

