In Phase 3a, which expands the enrollment further to include 600 participants, who will be randomly assigned 3:1 to receive ARCT-154 or placebo (450:150) for the initial series of vaccinations. After completion of enrollment of Phases 2 and 3a, the SRC and MOH will independently review available blinded safety data through at least 7 days (Day 8) post-first vaccination and, if study vaccination is judged to be adequately tolerated by SRC and the MOH, the study will initiate enrollment of Phase 3b. The second dose of study vaccine will not be administered to participants in Phase 3b until the SRC has reviewed the Phase 2 and Phase 3a safety data through 7 days post-second vaccination (Day 36) and judged that study vaccine is adequately tolerated. Data from participants in Phase 1, Phase 2, and Phase 3a will be pooled for a primary analysis of immunogenicity at Day 57. Data from this analysis will be submitted to the Vietnamese Ministry of Health for evaluation for potential emergency use authorization (EUA). Data from Phase 2 and 3a will also be pooled to allow comparison of immunogenicity following the 3rd dose (immune responses at Day 120 with that after the 2nd dose (immune responses at Day 57).

In Phase 3b, approximately 16,000 participants will be randomly assigned 1:1 to receive ARCT-154 or placebo for the initial series of vaccinations. Phase 3b constitutes the Exploratory

Efficacy Subgroup. Data from this subgroup will support regulatory filings along with immunogenicity data from Phase 1/2/3a and 3c. Participants in this Phase 3b portion of the study will contribute substantially to the safety analyses of ARCT-154.

Phase 3c will enroll approximately 2,400 participants randomized 1:1 to receive ARCT-154 or ChAdOx1. A subset of these enrolled participants (the first 1,500 participants enrolled in Phase 3c) will form an Immunogenicity Noninferiority Subgroup (Phase 3c-1); the remaining ~900 participants will form Phase 3c-2. Day 57 data from 800 participants in this Subgroup will be used to establish the noninferiority of immunogenicity of ARCT-154 vaccine as compared to ChAdOx1, a licensed comparator vaccine. These data, along with an analysis of safety from participants exposed to ARCT-154 and followed for a median period of 2 months (60 days) may be submitted to health authorities for evaluation for a Marketing Authorization or EUA dependent on jurisdiction.

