4.5.2 Randomization and Enrollment

Phase 1, 2 and 3a participants will be randomly assigned 3:1 (ARCT-154:placebo), while Phase 3b participants will be randomly assigned 1:1 (ARCT-154:placebo).

- Participants in Phase 1 and 3b will receive two doses of one type of study vaccine on Day 1 and 29 (ARCT-154 or placebo) and then two doses of the opposite vaccine (placebo or ARCT-154) on Day 92 and 120 (referred to as ‘Switchover’).
- Participants in Phase 2/3a who received ARCT-154 in the initial two-dose vaccination series will be further randomized to receive either ARCT-154 or placebo (in a 3:1 ratio) at Day 92 followed by placebo at Day 120. Participants that received placebo in the initial vaccination series will undergo Switchover to receive ARCT-154 at Day 92 and Day 120.

Phase 3c participants will be randomized 1:1 to receive ARCT-154 or ChAdOx1; no Switchover will occur for Phase 3c participants as all participants in this cohort receive active vaccine.

For Phases 2, 3a, 3b and 3c, prior to randomization, participants will be stratified by the following 3 stratification factors:

- Age < 60 at high risk of severe COVID-19
- Age < 60 not at high risk of severe COVID-19
- Age \geq 60 years of age (considered at risk of severe COVID-19 by default)

Participants will be defined as “at risk” if they are 60 years of age or older OR have medical history described as putting an individual at risk or possibly at risk of severe coronavirus disease 2019 (COVID-19) ([Appendix 5](#)).

As the eligibility criteria for Phase 1 exclude participants \geq 60 years of age or otherwise at risk for severe COVID-19, stratification will not occur for Phase 1.

At screening, a Participant Identifier will be assigned by the site via the Interactive Response Technology (IRT) system. After the participant has completed screening and is determined to be eligible for study participation, the participant will be randomized by the site via the IRT system. At randomization, the participant will automatically be assigned to a study group. This participant’s randomization must be documented in the Screening and Enrollment Log.

Randomization in IRT can be performed by the site via the internet by the investigator or site personnel (as delegated by the investigator) who are permitted by institutional policy and trained to perform this task.

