### Sample Size for Phase 3c Substudy

The primary safety endpoints of Phase 3c will be conducted in the Phase 3c Safety Analysis Set and Phase 3c Reactogenicity Analysis Set. With a sample size of approximately 2,400 participants randomized and with approximately 1,200 participants randomized in the study to receive ARCT-154 or ChAdOx1 for the safety analysis, based upon the following formula, if the incidence rate of an adverse event is 0.1%, the probability to detect one event in 1,200 vaccinated participants is 69.9% and if the incidence rate is 1.0% the probability is more than 99%:

$$p = 1 - (1 - R)^N$$

where R = incidence rate and N = sample size

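### Phase 3c non-inferiority power: the protocol's own inputs give about 66% with 800 participants, not more than 90%

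*Protocol*

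**What the plan says.** Protocol Section 8.5.3 gives the assumptions for the primary non-inferiority comparison of neutralizing antibody (pseudovirus MNT) at Day 57: a true GMR of 0.9 or more, a CV of 4.6, a margin of 0.67 and a one-sided test at 0.025. It concludes that "a sample size of 800 participants in Phase 3c-1 will provide greater than 90% power to exclude a non-inferiority boundary of 0.67". The Statistical Considerations part of the synopsis has the same sentence: "a coefficient of variation of 4.6, a sample size of 800 participants in Phase 3c-1 will provide greater than 90% power". Both add that the figure is "accounting for a dropout rate of approximately 20-25% due to the national COVID-19 vaccination campaign in Vietnam".

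Other sections fix what 800 means. Section 4.5.2 says "Phase 3c participants will be randomized 1:1 to receive ARCT-154 or ChAdOx1". Section 4.4 says "Day 57 data from 800 participants in this Subgroup will be used to establish the noninferiority of immunogenicity", and Section 4.1 agrees. Section 3.3.1 puts Phase 3c-1 enrolment at about 1,500 and adds "Samples from the remaining 700 participants in Phase 3c-1 will be retained for potential future immunological testing". So 800 is a total over both arms, taken from about 1,500, and these sections read as if it is the number analysed.

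The final SAP does not carry the calculation forward. Its Phase 3c sample-size text in Section 6.1 covers safety only: "The primary safety endpoints of Phase 3c will be conducted in the Phase 3c Safety Analysis Set and Phase 3c Reactogenicity Analysis Set". Sections 6.5 and 7.1 state that the Phase 3c immunogenicity samples were not tested and will not be analysed.

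**The concern.** A CV of 4.6 means a standard deviation 4.6 times the mean, which is very wide. The distance from an assumed ratio of 0.9 to a margin of 0.67 is only about 0.30 on the natural-log scale. With that spread, 400 per arm looks too few for 90% power.

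This is the only power statement for the Phase 3c primary immunogenicity objective. Section 4.4 says the result could go to health authorities in support of a Marketing Authorization or EUA. A reader of the protocol would believe that the test had less than a one-in-ten chance of missing non-inferiority at the assumed GMR of 0.9.

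**Working it through.** **Inputs**, all from Protocol Sections 8.5.3, 8.4.3 and 4.5.2: GMR 0.9 (the lower end of the stated range, where the claim must still hold), margin 0.67, CV 4.6, one-sided alpha 0.025, 800 in total at 1:1, so n = 400 per arm. All 800 are taken as evaluable, which is the reading of 800 most favourable to the protocol.

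**Step 1, scale.** For log-normal data, SD(ln) = √ln(1 + CV²) = √ln(1 + 4.6²) = 1.7602.

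**Step 2, distance to the margin.** ln(0.9/0.67) = 0.2951.

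**Step 3, power.** Power = Φ(0.2951 / (SD × √(2/n)) − 1.96). With n = 400, the standard error is 1.7602 × 0.07071 = 0.1245, and 0.2951/0.1245 − 1.96 = 0.411. Φ(0.411) = 0.660. The noncentral t distribution gives 65.8%. The stated figure does not reproduce.

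**Step 4, other readings, 800 in total and GMR 0.9 unless stated.**

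| Reading | SD(ln) | Power |
|---|---|---|
| CV 4.6, as written | 1.7602 | 66.0% |
| 4.6 is a geometric SD, SD(ln) = ln 4.6 | 1.5261 | 78.1% |
| 4.6 is the SD on the ln scale | 4.6 | 14.6% |
| CV 46% | 0.4381 | >99.99% |
| CV 4.6% | 0.0460 | >99.99% |
| CV 4.6, one-sided alpha 0.05 | 1.7602 | 76.6% |
| CV 4.6, margin 2/3 | 1.7602 | 67.4% |
| CV 4.6, true GMR 1.0 | 1.7602 | 89.6% |

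The two percentage readings exceed 90%, but at 46% only 47 per arm (94 in total) would be needed, and at 4.6% no more than 3 per arm, so 800 would have no rationale. At CV 4.6 and 800 in total, 90% needs a true GMR of about 1.003. Reading 800 as per arm would give 91.8%, but Sections 3.3.1 and 4.1 rule that out.

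**Step 5, size needed for 90%.** n per arm = 2 × SD² × (1.96 + 1.2816)² / 0.2951².

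- CV 4.6: 747.6, so 748 per arm, 1,496 evaluable.
- Geometric SD 4.6: 561.9, so 562 per arm, 1,124 evaluable.

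Conversely, 400 per arm reaches 90% only if SD(ln) is at most 1.2875, a CV of about 2.06.

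**Step 6, where the figure may come from.** The claim does reproduce at about 1,500, the full Phase 3c-1 enrolment. With CV 4.6 and no loss, 750 per arm gives 90.1%. With a geometric SD of 4.6, 1,500 less 20-25% leaves 600 to 562.5 per arm and gives 91.8% to 90.0%. This suggests that the sentence was not recalculated when the tested number became 800. The documents do not confirm it.

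**Step 7, dropout (secondary).** If the 20-25% loss comes off the 800, leaving 640 to 600, power falls to 56.4-53.7% (CV) or 68.7-65.9% (geometric SD). Sections 3.3.1, 4.1 and 4.4 favour 800 as the analysed number, so the conclusion does not use these figures.

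**The case against.** The strongest objection is that four printed numbers (GMR, CV, sample size, power) are inconsistent and nothing in the documents shows which is wrong. The wording around the CV in Section 8.5.3 is garbled, with a phrase repeated, and no scale is given. The CV could be the misprint and the power correct. As an illustration that is not in the documents, an SD of 0.46 on the log10 scale (1.059 on the ln scale) would give 97.6% with 800 evaluable and 92.7-94.1% after 20-25% loss, which would fit the whole sentence.

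This stands as a reason not to assert that the true design power was 66%. It does not rescue the sentence: no such SD appears anywhere, and a power claim has to follow from the assumptions printed beside it. It is also why the fix lets the sponsor confirm the scale of 4.6 or withdraw the statement.

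The second objection is that the statement no longer has a function. The final SAP removes the Phase 3c immunogenicity analysis and gives its reasons in Section 7.1. This also stands, and it limits the consequence: no planned result depends on the figure. But the SAP records only that the analysis was dropped, and the protocol still shows the uncorrected power for a primary objective.

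**Conclusion.** The concern holds. On the protocol's stated inputs, with all 800 participants evaluable and a true GMR of 0.9, power is 66.0%, at least 24 percentage points below the claim. The test as planned would miss non-inferiority about one time in three. If 4.6 is a geometric SD, power is 78.1% and the shortfall is at least 12 points. No plausible reading of 4.6, with 800 in total, supports more than 90% at GMR 0.9.

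The result rests on log-normal concentrations, equal variance and size in the two arms, and the CV as printed. Confidence is high that the sentence is wrong as written. The cause is not established. The practical effect is confined to a stated design property in two places in the protocol.

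**What to change.** In Protocol Section 8.5.3 and the matching synopsis sentence, do one of the following:

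- Replace the power claim with about 66%, stating that it applies to 800 evaluable participants, GMR 0.9 and CV 4.6. If the sponsor confirms that 4.6 is a geometric SD, say so and give about 78%.
- Withdraw the power statement, noting that the final SAP no longer analyses Phase 3c immunogenicity.

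If the sentence is kept, say whether 800 is before or after the 20-25% dropout.

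The cost is wording only. It needs no new participants, no further sample testing and no change to any planned final analysis. The stated power becomes less favourable.
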